# **Study summary**

Study Title	The Sickle Eye Project: Prevalence of visual impairment due to sickle cell retinopathy and maculopathy in the United Kingdom	
Short title	The Sickle Eye Project	
Study Design	Cross-sectional, non-interventional study	
Study Participants	People with Sickle cell disease	
Planned Size of Sample (if applicable)	600 patients with sickle cell disease	
Planned recruitment Period	12 months	
Research objectives	
 
Primary objective: To determine the prevalence of visual impairment (best corrected visual acuity ≥ LogMAR 0.3 in at least one eye) due to sickle cell retinopathy (SCR) and/or maculopathy in persons with sickle cell disease (SCD)
 
Secondary objectives:         
 
To determine the prevalence of each stage of SCR and maculopathy and correlation with:                   

	

# 1. Introduction

# 1.1 Proliferative sickle cell retinopathy

Sickle-cell disease (SCD) is one of the most common genetic disorders in the UK, with approximately 15000 people affected. It is a debilitating, multisystem disease, associated with episodes of acute illness, progressive organ damage and reduced life expectancy. There are 13 genetic variants of SCD, with HbSS genotype being most common (>70%) and most severe, followed by HbSC genotype. SCD affects predominantly people of African and Afro-Caribbean descent and evidence demonstrates inequalities in healthcare outcomes and access for people with SCD . An all-party parliamentary group inquiry reported low awareness of SCD and its complications among healthcare professionals and underinvestment in sickle cell research.

Proliferative sickle cell retinopathy (SCR) is the most common ophthalmic manifestation of SCD and can result in significant sight loss, although the prevalence in the U.K is not currently known. Decades old retrospective and cohort studies from other countries have estimated prevalence of SCR in SCD patients at up to 48% and associated with significant sight loss in up to 12%. Importantly, life expectancy for SCD has increased from 14 years in 1973 to >60 years in high-income countries with improvement in management and healthcare delivery. Evidence from cohort studies and large retrospective studies demonstrate increasing incidence of SCR with age. As such, we could expect the prevalence of SCR and potentially associated visual impairment, to be currently higher in the UK than previously reported.

Five stages of SCR were described by Goldberg in 1971. These are progressive with stages 1-3 being asymptomatic, stage 3 reflecting the presence of retinal neovascularisation in the far periphery known as seafan neovascularisation, vitreous haemorrhage (bleeding inside the eye) develops in stage 4 and rhegmatogenous and/or tractional retinal detachment in stage 5.

#### 1.2 Sickle cell maculopathy

In addition to the peripheral retina, SCD can also affect the macula (central retina) potentially causing visual loss, known as sickle cell maculopathy. Sickle cell maculopathy (SCM) is defined as patchy areas of severe retinal thinning in the temporal macula. The exact aetiology of macular thinning remains unclear, but it may be related to the temporal macula ending along the horizontal raphe, making it a watershed zone between the vascular arcades of the retinal circulation and thus more susceptible to vascular occlusions. Whilst high-contrast visual acuity was preserved in most patients demonstrated to have SCM in a single centre study, irreversible scotoma, decreased retinal sensitivity and visual loss has been described in association with SCM. Maculopathy was not included in the Goldberg classification as its presence only became more apparent with modern imaging techniques. There is currently no treatment for vision loss due to maculopathy.

# 1.3 Current interventions for SCR and maculopathy

Laser photocoagulation is currently the only intervention with high-level evidence of safety and efficacy in the management of stage 3 SCR. Laser photocoagulation has an indirect effect as it destroys the ischaemic retina responsible for production of vascular endothelial growth factor (VEGF) that triggers the proliferation of new blood vessels. This technique is commonly used in the treatment of diabetic retinopathy and widely available in the U.K. For SCR, there has been a paucity of randomized controlled trials (RCT) of intervention, with only 2 RCTs evaluating laser treatment for stage 3, and both conducted over 30 years ago. In the first randomized controlled trial of laser, Jampol et al compared laser treatment to observation in a randomized controlled trial of 167 eyes and reported 3.4% developed vitreous haemorrhage (stage 4 SCR) in the laser-treated arm versus 27.5% in the observation arm whilst 1% developed visual loss in the laser-treated arm versus 5% in the observation arm. Faber et al subsequently reported similarly positive results; with a Cochrane review of the safety and efficacy data of laser treatment for stage 3 SCR concluding that laser treatment reduces the risk of visual loss at mean follow-up of 1 year and is protective against the development of vitreous haemorrhage. However, the RCTs and other case series also reported spontaneous regression of stage 3 in up to 30% of eyes. In addition, these RCTs evaluating laser treatment are more than 30 years old and laser technology as well as the systemic management of SCD has improved significantly in that time.

Alternatively, stage 3 and 4 SCR can be managed with intravitreal anti-vascular endothelial growth factor (anti-VEGF) therapy. Over the last 16 years, intravitreal anti-VEGF have become common place in ophthalmic practice with many licensed indications including age-related macular degeneration and diabetic retinopathy. As VEGF is implicated in SCR^18, the use of intravitreal anti-VEGF therapy is scientifically rational, and evidence of regression and resolution has been demonstrated in case series of eyes with stage 3 and 4 SCR^19. Additionally, angiopoietin-1 and angiopoietin-2 have also been implicated in the pathophysiology of SCR^20. In June 2022, NICE approved Faricimab, an intravitreal bi-specific monoclonal antibody that inhibits VEGF and angiopoietin-2 for the treatment of wet-age related macular degeneration and diabetic macular oedema. No RCTs have been conducted comparing intravitreal anti-VEGF therapy or anti-angiopoietin-2 to laser therapy or observation.

The main therapeutic intervention for stage 4 and 5 SCR is vitrectomy. Vitrectomy is a surgical intervention that involves removal of the vitreous (including blood if stage 4 SCR) and repositioning of the retina to its proper position against the back of the eye (when there is retinal detachment as in stage 5). Despite significant advances in modern surgical techniques, visual outcomes for stage 4 or 5 SCR remain poor, with final visual acuity post-surgery often significantly below driving vision,  so early detection of SCR remains an opportunity to prevent sight loss.

There is also the potential for systemic treatment of SCD to influence the progression of SCR and/or maculopathy. Hydroxycarbamide is the gold standard treatment for prevention of painful crises in SCD and has

been proven to reduce hospital admissions in patients with SCD. Hydroxycarbamide induces fetal hemoglobin production (HbF) thereby decreasing sickle hemoglobin erythrocyte polymers, haemolysis, and painful vaso-occlusive crisis. Rigorous investigation over the past 30 years has demonstrated the efficacy of hydroxycarbamide in reducing disease complications, health care utilization, and costs for patients with SCD. However, compliance rates are well established to be low and linked to a variety of reasons including fear of side effects, stigma and low health literacy. Although there are no prospective studies that evaluate the efficacy of hydroxycarbamide on reducing the incidence of SCR, large retrospective studies have highlighted the protective effect of hydroxycarbamide on SCR and maculopathy. These studies suggest hydroxycarbamide, by elevating levels of HbF, can significantly reduce the odds of developing SCR and reduce the progression of sickle maculopathy. There is also emerging evidence that the severity of SCR and maculopathy correlates with severity of systemic anaemia associated with SCD. As such, retinal screening may improve compliance with hydroxycarbamide if evidence confirming protective retinal effects are corroborated. Retinal screening may also highlight the need for escalations of management to the haematologist.

#### 1.4 Retinal imaging for SCR and maculopathy

Retinal imaging has undergone revolutionary advancement in the past 20 years. Ultrawide field fundus photography detects SCR more reliably than traditional eye examination or imaging. The widespread availability and use of optical coherence tomography (OCT) (and OCT-angiography in some centres), which are rapid, non-invasive imaging tools that produce detailed images of the macular and associated vascular plexuses means we can now detect damage to the macular otherwise undetected using traditional methods. These tools are now used routinely and extensively in the management of various high-volume eye diseases across the country including age-related macular degeneration, diabetic eye disease and patients with visual symptoms from SCR or maculopathy and are likely to be acceptable to all patients with SCR. The combination of Ultrawide field colour, OCT and OCTA will provide the best method for detecting vision-threatening retinal changes in sickle cell disease and detecting change over time.

### 1.5 Clinical study rationale

There is no reliable estimate of the burden of sight loss due to SCR and maculopathy in the UK or the number of people with different stages of SCR and maculopathy. This lack of data makes planning configuration and delivery of appropriate services for eye health in SCD difficult and could lead to unwarranted variation

There is also no national screening guideline or programme for early detection of SCR in the U.K. The National Institute for Health and Care Excellence (NICE) recommends that people with SCD should be evaluated by an ophthalmologist every 2-3 years if they have no evidence of retinopathy and people with retinopathy should be reviewed at least annually. However, only 40% of eye departments provide routine retinal screening for SCR in a recent feasibility survey of eye departments in the UK ([name], 2022, unpublished) due to lack of consensus

on appropriate intervention to prevent progression. In centres providing screening there is variation in how this is undertaken between clinical examination and type of retinal imaging used. Our study will determine the proportion of vision loss due to SCR and maculopathy in the U.K. We will also determine the distribution of the stages of SCR and maculopathy and correlation with severity of SCD. SCR and maculopathy screening are easily incorporated into existing diagnostic clinic pathways for retinal diseases. However, there is a need to establish any benefit of screening and the acceptability to patients with SCD.

We do not currently know what the prevalence of sight loss due to SCR and maculopathy is, nor the potential for preventing sight loss by implementing a national screening programme. The traditional approach of face to face clinic appointment can also make compliance difficult in a working age population with many health demands. The use of imaging could provide a more flexible approach to access, through diagnostic centres as has been introduced in Newcastle where virtually all the sickle cell patients under the care of haematology have now had their eyes imaged.

Our patient and public involvement (PPI) group informed us of their lack of awareness of the potential effects of SCD on vision. They described the difficulties associated with vision loss including the increased vulnerability associated with loss of driving license in the context of living with SCD, days off work associated with vitreous haemorrhage impacting their financial well-being and livelihoods and difficulty engaging in vision-related tasks at work and university. One of the members of our PPI group told us they would have been compliant with their systemic medication if they knew it could help preserve their sight and the others agreed this could be a motivating factor for many people with SCD.

### 2.Study Objectives

The Sickle Eye Project includes an internal pilot phase, which is the first 4 months of the recruitment period, to assess recruitment and trial processes.

The objectives of the internal pilot are:

- 1. To open 6 sites by the end of the pilot phase
- 2. 95% of the expected monthly recruitment is achieved by the end of the pilot phase
- 3. Adherence to imaging protocol in ≥90% of cases
- 4. 95% of recruited participants with completed NEI VFQ 25 questionnaire

Main study primary objective: To determine the prevalence of visual impairment (best corrected visual acuity ≥LogMAR 0.3 in at least one eye) due to SCR and/or maculopathy in persons with SCD

Main study secondary objectives:

- 1. To determine the prevalence of each stage of SCR and maculopathy and correlation with:
- i) number of hospital admissions with acute sickle cell episode in the past 12 months, ii) serum HbF level iii) serum Hb level
- 2. To determine the impact of SCR and maculopathy on vision-related quality of life.
- 3.To determine the acceptability to patients of retinal imaging and routine screening for SCR and maculopathy.

#### 2.1 Outcome measures

#### Internal pilot outcomes

The following progression criteria using a red/amber/green traffic light system will be used to inform whether we progress to the main trial:

## Site opening progress

Green: 6 sites are open to recruitment

Amber: 3 -5 sites are open to recruitment

Red: 2 or fewer sites or more are open to recruitment

# Recruitment progress

Green: Recruitment of >120 at end of pilot phase

Amber: Recruitment of < 120 but ≥ 79 patients at end of pilot phase

Red: Recruitment of <79 patients at end of pilot phase.

### Fidelity check demonstrating adherence to image acquisition protocol

Green: Adherence to image acquisition protocol in ≥90% of cases.

Amber: Adherence to image acquisition protocol in ≥80%

Red: Adherence to image acquisition protocol in <80% of cases

#### Completion of the NEI VFQ-25

100% of recruited participants completing the NEI VFQ-25

Green: ≥95% of recruited participants with completed NEI VFQ-25

Amber: ≥80% of recruited participants with completed NEI VFQ-25

Red: <80% of recruited participants with completed NEI VFQ-25

If at the end of the pilot phase the thresholds are at amber or red for any of the progression decision points, the Co-Investigator Group, which includes a lived experience expert as co-applicant will review and provide remedial action that would allow progression to the main trial to the Funder. If there are no obvious remedial actions that can be taken, the Co-Investigator group will discuss stopping the trial with the Funder.

#### Main study primary outcome

1. The prevalence of visual impairment due to SCR or maculopathy (defined as best corrected visual acuity LogMAR ≥ 0.3 in at least one eye) in a representative sample of the UK population with SCD

#### Secondary outcomes

- 1. The prevalence of each stage of SCR and presence of maculopathy by age and genotype
- 2. The correlation of each stage of SCR and maculopathy to severity of SCD as determined by number of hospital admissions in the preceding 12 months/serum HbF/ serum Hb.
- 3. The impact of SCR and presence of maculopathy on vision-related quality of life.
- 4. The acceptability to patients of routine retinal imaging for SCR and maculopathy
- 5. The development of updated consensus definitions and a modernized classification system for SCR and maculopathy, leveraging the increased insight into retinal tissue anatomy and vascular blood flow afforded by contemporary imaging technologies

### 3. Overall study design

## 3.1 Study design

This is a cross-sectional, non-interventional study. Potential participants will be introduced to the study by their haematologist, who will also provide them with the participant information sheet. Identification of potential participants in the haematology clinic is important to prevent ascertainment bias and sample a representative

sample of people with SCD. All patients with SCD are offered regular specialist follow-up by a haematologist in the UK. The national haemoglobinopathy registry record for 2021 reported 12904 people with SCD confirming that an overwhelming proportion of SCD patients are under specialist care in the UK. Informed consent will be obtained from willing participants by the ophthalmology team either in the eye department or over the telephone. Informed consent will be obtained prior to the collection of any data. Once consented, participants will have best corrected visual acuity (BCVA) with habitual correction and pinhole measured, a slit lamp examination of the anterior segment and fundus, spectral-domain optical coherence tomography (SD-OCT), optical coherence tomography-angiography (OCT-A) and ultra-widefield fundus photography performed in the eye department. Subsequently, the participant will have the NEI VFQ-25 questionnaire and the acceptability of retinal screening questionnaire administered.

In some departments, it may be more appropriate for the haematology team to share brief details about the study, including the study leaflet with potential participants. Interested participants can be sent the participant information sheet ahead of their eye clinic appointment.

The NEI VFQ-25 questionnaire can be administered over the telephone either at the time of consent or after the visit to the eye department. The acceptability of retinal screening questionnaire has to be administered after the retinal imaging has been performed.

If the NEI VFQ-25 is completed over the telephone, this must be done ±28 days of the eye clinic visit for examination and retinal images.

The research team will also complete an electronic case report form recording basic demographic history such as: Year of birth, Sex, Sickle genotype, Number of hospital admissions with acute sickle crisis, medical history, current medications and interventions for SCD, previous history of stage 4 or 5 sickle cell retinopathy, ocular comorbidities, previous ocular interventions and most recent serum haemoglobin (Hb) and serum haemoglobin F (HbF) within 3 months of study entry.

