# Slit lamp biomicroscopy and dilated funduscopy

Slit lamp biomicroscopy allows the ophthalmologist to microscopically examine the eye for any abnormalities or problems. Dilated funduscopy allows better evaluation of the lens and vitreous. This will be performed to document other ocular causes of visual impairment such as corneal scars, cataracts and vitreous haemorrhage.

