### Ultra-widefield fundus photography

Ultra-widefield fundus photography captures an image covering more than 80% of the retina. It allows the observer to assess the retina, associated blood vessels and optic nerve. This is particularly of benefit in sickle cell retinopathy, where the initial stages of proliferative retinopathy occur in the far periphery and can be missed if the periphery is not carefully assessed. In the UK, Optos imaging and the Zeiss Clarus are the most commonly used ultra-widefield imaging systems. All units included in this study will be using either the Optos or the Clarus. Whilst there is evidence that un-dilated ultrawide field fundus photography can be of utility in screening for sickle cell retinopathy with a specificity of 100% compared to dilated funduscopy examination in one study, the sensitivity was 69.2%. Therefore, for the purpose of this study, ultra-widefield fundus photography will be performed with a dilated pupil. All images will be assessed by the ophthalmology team and management instituted as per standard of care. The interpretation of the images will be documented in the study case report form

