# EQ-5D with vision bolt-on

The 5 level EQ-5D is a widely used preference-based health related quality of life instrument with one question for each of 5 core dimensions of health: mobility, self-care, usual activities, pain/discomfort and anxiety/depression. To capture the effect of conditions that affect sensory functions or cognition that may not

be adequately captured by the instrument, additional dimensions, known as 'bolt-ons' were developed. The vision bolt-on has demonstrated enhanced sensitivity, construct validity and responsiveness to change in populations with vision problems. Importantly, EQ-5D with vision bolt-on comprises of 6 questions which can be rapidly completed by participants

Study activity	Personnel	Baseline	±28 days
Eligibility	Haematology team		
criteria check		X	
		*	
Patient	Haematology team	х	
information	Or Ophthalmology team		
sheet	er opmilainiology toain		
Informed	Ophthalmology team	x (Can be completed by	
consent		telephone)	
BCVA with	Ophthalmology team	х	
habitual			
correction and			
pinhole			
Slit lamp	Ophthalmology team	X	
biomicroscopy			
and dilated			
funduscopy			
ОСТ	Ophthalmology team	х	
OCT-A	Ophthalmology team	Х	
Ultrawide field	Ophthalmology team	х	
fundus			
photography			
*NEI-VFQ 25	Ophthalmology team	x (Can be completed by telephone)	Х

*Acceptability	Ophthalmology team	x (Can be completed by	Х
Questionnaire		telephone after retinal	
		imaging and within 14 days)	
Clinical	Ophthalmology	X	
assessment of			
images			
Completion of	Ophthalmology/haematology	Х	Х
case report	team		
form			
Transfer of	Ophthalmology team	X	Х
images			

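### The NEI VFQ-25 has no fixed place relative to pupil dilation, feedback of findings and treatment, and the acceptability questionnaire carries two different upper time limits

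*Protocol*

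**What the plan says.** **NEI VFQ-25.** Protocol 3.1 lists acuity, slit lamp and fundus examination, OCT, OCT-A and ultra-widefield photography, and continues: "Subsequently, the participant will have the NEI VFQ-25 questionnaire and the acceptability of retinal screening questionnaire administered". Section 3.5.3 makes the funduscopy a dilated one ("Dilated funduscopy allows better evaluation of the lens and vitreous") and says that "ultra-widefield fundus photography will be performed with a dilated pupil". Section 3.1 then adds a second route: "The NEI VFQ-25 questionnaire can be administered over the telephone either at the time of consent or after the visit to the eye department". It bounds that route: "If the NEI VFQ-25 is completed over the telephone, this must be done ±28 days of the eye clinic visit for examination and retinal images".

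**Feedback and treatment.** Section 3.5.3 says under each imaging modality: "All images will be assessed by the ophthalmology team and management instituted as per standard of care". It does not say whether this comes before or after the questionnaires.

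**Acceptability questionnaire.** Section 3.1 states: "The acceptability of retinal screening questionnaire has to be administered after the retinal imaging has been performed". It gives no upper limit. In the activity table that closes section 3.5.3, the baseline cell allows telephone completion after "imaging and within 14 days", and the same row is also marked in the ±28 days column.

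**Use.** Section 5.1 plans Spearman correlations of the NEI VFQ-25 global score and of acceptability with acuity, SCR stage and presence of maculopathy. It makes no distinction by when the form was completed. These serve secondary outcomes 3 and 4 in section 2.1.

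**The concern.** The NEI VFQ-25 asks about visual function and its effect on daily life. A participant on the default clinic route answers while dilated. One telephoned after the visit may already have been told the findings, or have been treated. One telephoned at consent has experienced neither. Stage and acuity are taken from the visit in every case.

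This is more than random noise, because what a participant is told depends on stage and so does the chance of treatment. Section 1.1 calls stages 1 to 3 asymptomatic, and section 1.5 reports that the patient group did not know sickle cell disease could affect vision. A lower score that follows from being told of retinopathy would be read as an effect of the retinopathy on quality of life. Treatment before a late call could move scores at the severe end in either direction. Analysis cannot recover a pre-disclosure score that was never collected, so the visit order has to be settled in the protocol.

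For the acceptability questionnaire the stake is smaller: a site cannot tell whether a form completed on days 15 to 28 is valid.

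**Working it through.** **1. Times at which an NEI VFQ-25 may be completed (day 0 = eye visit)**

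| Route | Day | Relative to dilation | Relative to feedback or treatment |
|---|---|---|---|
| Telephone at consent | −28 to 0 | before | before |
| In clinic, default order | 0 | after | not stated |
| Telephone after the visit | 0 to +28 | after | may follow either; nothing excludes it |

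The telephone window spans 28 + 28 = 56 days. Forms from all three rows enter the same correlation in section 5.1.

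**2. Acceptability window**

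- Section 3.1: after imaging, no upper limit.
- Activity table, baseline cell: after imaging, day 0 to +14.
- Activity table, second column: ±28 days. Combined with the after-imaging rule, this leaves day 0 to +28.
- Days allowed by one entry and barred by the other: 28 − 14 = 14 (days +15 to +28).

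**3. How many participants could be affected by disclosure**

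From the protocol's illustrative stage table in section 5:

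- Stages 1 to 3: 222 + 110 = 332 of 554, or 60%.
- Any SCR: 222 + 110 + 28 + 28 = 388 of 554, or 70%.

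**4. Illustration of size (assumptions, not protocol figures)**

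Suppose that disease has no true effect on the score, that being told of SCR lowers it by d standard deviations, and that a share f of participants with SCR answer after newly learning of it. The mean shift in the SCR group is then D = f × d. With 70% having SCR, the correlation of score with any SCR has absolute size approximately

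r = D × √(0.7 × 0.3) / √(1 + 0.21 × D²), and in standard errors atanh(r) × √(554 − 3).

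| d | f = 1: r (SE) | f = 0.5: r (SE) |
|---|---|---|
| 0.1 | 0.05 (1.1) | 0.02 (0.5) |
| 0.2 | 0.09 (2.1) | 0.05 (1.1) |
| 0.3 | 0.14 (3.2) | 0.07 (1.6) |

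The f = 1 column is a ceiling, since it has every participant with SCR answering after a new diagnosis. It also uses SCR as yes/no, whereas the plan correlates with ordinal stage. The table shows only that the result runs from negligible to noticeable, depending on quantities the documents do not give. The effects of dilation and treatment are not quantified here, because no treatment rate or share of post-visit calls is stated.

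**The case against.** The protocol supports less than a quick reading suggests, on four counts.

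- **Image reading before the questionnaire.** A reader might infer that the NEI VFQ-25 is scheduled after the images are read. No text says so. The activity table lists clinical assessment of images below both questionnaires and sets no order within the visit. The telephone-at-consent route also means timing is mixed rather than always late. This objection stands.
- **Acceptability before imaging.** A reader might take the minus side of the ±28 days column as permission. Section 3.1 and the table cell both require completion after imaging. The column also carries case report form completion and image transfer, and the asterisk on the questionnaire rows has no footnote in the text available. The mark cannot be read as overriding two explicit statements. Only the upper limit is in doubt.
- **Telephone consent long before the visit.** A reader might think the at-consent option breaks the ±28-day rule. It does not: the rule governs all telephone completion, so a call more than 28 days ahead is already out of window and a later route remains.
- **Size.** The 0.1 to 0.3 SD shifts have no basis in the documents. Some participants will already know their eye status: sites may already run screening (section 3.4's preceding section, 3.2), and the case report form records previous stage 4 or 5 disease and eye interventions (3.1). This stands, and it is why no bias estimate is claimed.

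There is also a practical objection. Section 3.5.3 notes that the questionnaire can take up to 15 minutes and may limit recruitment, and 95% completion is the green pilot criterion in section 2.1. Removing post-visit calls could hurt both. That is a fair reason to keep them as a fallback, but it does not justify leaving the order unspecified.

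**Conclusion.** The point holds in limited form. The default clinic order places the NEI VFQ-25 after a dilated examination and imaging. The telephone options place it anywhere from 28 days before the visit to 28 days after, and no rule ties it to feedback or treatment. Because disclosure and treatment depend on stage, pooling these forms could distort the correlation used for secondary outcome 3. The direction and size are unknown. They depend on the share of forms completed after feedback, how many participants newly learn their stage, and how far that moves the score, and the protocol gives none of these.

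For the acceptability questionnaire, the 14-day and ±28-day entries conflict over days 15 to 28. It would go too far to say this outcome is measured at the wrong time: it is required after imaging, as it should be, and nothing shows that a day 15 to 28 form would change the result.

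The primary outcome and the sample size are unaffected. The change is worth making because it is cheap and cannot be made retrospectively.

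**What to change.** In section 3.1 and the activity table:

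1. Give the NEI VFQ-25 after consent and before dilation and any discussion of findings, either on arrival or by telephone within the 28 days before the visit. The existing telephone-at-consent route shows that early completion is workable.
2. Keep completion within 28 days after the visit as a fallback, so that completion rates are protected. Record the completion date and flag these forms on the eCRF.
3. Repeat the quality-of-life analysis without the flagged forms.
4. Give the acceptability questionnaire one window that starts at imaging, choose a single upper limit, and make section 3.1, the table cell and the ±28 days column agree.

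The cost is protocol wording, a reordered visit, and a date and flag on the eCRF. The small downside is less flexibility for sites that rely on a post-visit call.
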